5.3 Screen Failures

Screen failures are defined as subjects who consent to participate in either the Phase III study or the Optional Maximal Use arm but do not meet the eligibility criteria. A minimal set of screen failure information is required to ensure transparent reporting of screen failure subjects to meet the Consolidated Standards of Reporting Trials (CONSORT) publishing requirements and to respond to queries from regulatory authorities. Minimal information includes demography, eligibility criteria, and any SAE will be collected and recorded in the electronic data capture system.

Individuals who do not meet the criteria for participation in the studies (screen failure) may be rescreened for the following circumstances:

- Subjects who fail to complete their washout in time for their scheduled Visit 2 (Baseline) can be allowed to continue the washout and Visit 2 may be rescheduled.

- Subjects who have a clinically non-significant out-of-range laboratory result may be rescreened one time.

Any subject who is rescreened is required to have a new informed consent form (ICF)/assent.

6 STUDY TREATMENT

6.1 Study Treatment(s) Administered

6.1.1 Treatment Area

The Treatment Area for each subject is defined as the area of the entire body with active CI where the study medication will be applied (the entire body [except for the hands, face, neck, scalp, inner thighs near genitalia and genitalia] are possible treatment areas).

6.1.2 Treatment Administration

Treatments administered during the Phase III study, including frequencies and durations are presented below in Table 5. Study medication will be applied to up to 90% of the BSA. Prior to randomization, the location of the CI to be treated and the percent BSA with CI in the Treatment Area (see [Section 8.2.3](#)) will be recorded.

6.1.2.1 Maximum Daily Dose

The approximate maximum daily doses expected are outlined below in Table 4. As study medication can be applied to up to 90% BSA twice daily, these parameters were calculated to estimate the maximum daily doses in pediatric and adult subjects.

Table 4 Maximum Daily Dose

	Height	Weight	BSA in m ²	90% BSA	Amount of Isotretinoin applied daily (TMB-001 0.05% at BID dosing)	Amount of drug/m ² applied daily with BID dosing
Average 6 year old	110cm	20.3kg	0.7799m ²	0.7019m ²	0.013g a day	0.019g/m ²
Average adult male	179cm	71.9kg	1.9002m ²	1.7101m ²	0.034g a day	0.020g/m ²

Treatment administration specific to the Optional Maximal Use arm is described in [Section 9.2](#).

Table 5 Treatment Administration

Study Period	Treatment Administration
Study Period 1 (Induction)	
 • TMB-001, 0.05%, QD for 3 weeks along with mandatory standardized bland emollient (Cetaphil™) provided by Sponsor • Vehicle ointment (Control) QD for 3 weeks along with mandatory standardized bland emollient (Cetaphil™) provided by Sponsor
Study Period 2 (Treatment)	
 • TMB-001 0.05% ointment BID for 9 weeks without mandatory emollients • Vehicle ointment BID for 9 weeks without mandatory emollients
Study Period 3 (Maintenance)	
 • TMB-001, 0.05%, QD or BID from Week 12 to 24 without mandatory emollients

Abbreviations: BSA = Body Surface Area; BID = Twice Daily; QD = Once a day; VIIS = Visual Index for Ichthyosis Severity

When applied BID, the study medication should be administered ideally once in the morning and once in the evening, but at least 6 hours apart. When applied QD, the study medication can be applied at any time of the day provided applications are separated by at least 12 hours.

Per protocol amounts of study medication to be applied based on subject's percent BSA are indicated in the Subject and Site Instruction Sheet as well as in the Subject electronic Diary (eDiary). The subject and parent/guardian (if applicable) will be instructed on how and where to dispense and apply study medication to the Treatment Area and to record applications in the Subject eDiary. Product application will be clearly demonstrated by the Investigator or a designated healthcare professional at the Baseline visit, and the subject and parent/guardian (if applicable) will be provided with a Subject Instruction Sheet.

Under all circumstances when emollients are mandated by protocol or required for treatment of LSRs, emollients should be applied either 3-5 hours prior to or following application of TMB-001 0.05% or Vehicle as applicable. Emollients under all circumstances should be withheld for 24 hours prior to any scheduled efficacy visits as outlined in the SoA (Table 1 and Table 13).

Study treatment details are provided in Table 6. The vehicle ointment contains only the inactive ingredients and color additive so that the active and vehicle formulations are indistinguishable.

Table 6 Study Treatments

Study Treatment Name:	TMB-001 0.05%	Vehicle
Dosage Formulation:	Ointment	Ointment
Unit Dose Strength(s)/Dosage Level(s):	0.05%	Not applicable
Route of Administration	Topical	Topical
Dosing Instructions:	Once a day (QD) for first 3 weeks then twice a day (BID) (morning and evening) for next 9 weeks, then QD or BID for 12 weeks (depending on randomization)	QD for first 3 weeks then BID (morning and evening) for next 9 weeks

Study Treatment Name:	TMB-001 0.05%	Vehicle
Packaging and Labeling	Study medication will be provided in aluminum tubes. Each aluminum tube will be labeled as required per country requirement.	Vehicle ointment will be provided in aluminum tubes. Each aluminum tube will be labeled as required per country requirement.
Storage Temperature	Store at 36°F to 46°F (2°C to 8°C) until assigned to study participant. Once assigned, store at 68°F to 77°F (20°C to 25°C), excursions permitted to 59°F to 86°F (15°C to 30°C).	Store at 36°F to 46°F (2°C to 8°C) until assigned to study participant. Once assigned, store at 68°F to 77°F (20°C to 25°C), excursions permitted to 59°F to 86°F (15°C to 30°C).
Manufacturer	[REDACTED] [REDACTED], USA	[REDACTED], USA

Note: Subjects in both the TMB-001 0.05% treatment and the vehicle treatment group will apply a bland emollient (Cetaphil™ Moisturizing Lotion) provided by the Sponsor during Study Period 1 (see [Section 4.1](#)).

6.2 Preparation/Handling/Storage/Accountability

TMB-001 0.05% ointment and vehicle ointment are manufactured in a current Good Manufacturing Practice (GMP)-compliant facility and tested prior to release to ensure that the quality characteristics of each clinical batch are met.

The study treatment will be shipped directly to the study site. The Investigator or designee must confirm that appropriate temperature conditions (Table 6) have been maintained during transit for all study treatments received and any discrepancies are reported and resolved before use of the study treatment.

At study time points indicated in the SoA ([Table 1](#) and Table 13), subjects will be given tubes of study treatment for dosing at home, sufficient for dosing between clinical visits. The dispensed tubes must be returned to the study center during the next in clinic visit where study treatment accountability will be performed by the site staff. The tubes will be weighed periodically as detailed in the IP Handling Guidelines.

Only subjects enrolled in the study may receive study treatment, and only authorized study center staff may supply or administer study treatment. All study treatments must be stored in a secure, environmentally controlled, and monitored (manual or automated) area in accordance with the labeled storage conditions with access limited to the Investigator and authorized study center staff.

The Investigator or designee is responsible for study treatment accountability, reconciliation, and record maintenance (i.e., receipt, reconciliation, and final disposition records) using the Drug Accountability Form. These forms must be available for inspection at all times.

Further guidance and information for the final disposition of unused study treatments are provided in the Investigator Study Binder.

6.3 Randomization

Subjects enrolled in the study who meet all inclusion criteria and none of the exclusion criteria will be randomized at Baseline (2:1 ratio) to either the TMB-001 0.05% or the vehicle treatment

group, stratified by age, and CI sub-type. At Week 12, eligible subjects in the TMB-001 0.05% treatment group will be randomized (1:1 ratio) to either TMB-001 0.05% QD or BID maintenance treatment ([Figure 1](#)).

All subjects will be centrally assigned to randomized study treatment using an Interactive Web Response System (IWRS). Before the study is initiated, the log in information and directions for the IWRS will be provided to each study center.

The Optional Maximal Use arm is open-label and does not require randomization.

6.3.1 Blinding and Unblinding

In the double-blind Induction and Treatment Period (Study Periods 1 and 2) of the study, all personnel involved, i.e., physicians, site staff, participants and Sponsor will remain blinded at all times, except in an emergency, where knowledge of the randomization code is required to provide appropriate treatment. In case of an emergency, the Investigator has the sole responsibility for determining if unblinding of a subject's treatment assignment is warranted. Subject safety must always be the first consideration in making such a determination.

If the Investigator decides that unblinding is warranted, every effort should be made to contact the Sponsor and Medical Monitor prior to unblinding a subject's treatment assignment unless this could delay emergency treatment of the subject. If a subject's treatment assignment is unblinded, the Sponsor must be notified within 24 hours after breaking the blind. The date and reason that the blind was broken must be recorded in the source documentation and electronic Case Report Form (eCRF), as applicable.

6.4 Study Treatment Compliance

The prescribed dosage, timing, and mode of administration may not be changed, except as defined in [Section 7.1](#). Any departures from the intended regimen must be recorded in the eCRF.

During the course of the study, compliance to study drug application will be evaluated via Subject eDiaries and accountability by the site. Subjects exhibiting poor compliance should be counseled on the importance of good compliance to the study dosing regimen.

6.5 Concomitant Therapy

Prohibited medication and treatments including the washout periods are summarized in Table 7.

- Non-petrolatum bland emollients^a and OTC low potency hydrocortisone (e.g., 1% cream) may only be used in the event of severe discomfort (e.g., burning/erythema/itch) (after Week 3 in the Phase III study and during the entire time in the Optional Maximal Use arm) and if it is the opinion of the Investigator that a drug interruption (per [Section 7.1](#))

^a Subjects enrolled in the study will use mandatory bland emollients during the Induction Period (1-3 weeks). After the Induction Period, bland emollients will be prohibited for these subjects until the EOS visit. Subjects enrolled into the Optional Maximal Use arm should discontinue the use of bland emollients at Visit 2 (Baseline).

alone will not relieve the symptoms and these may cause the subject to discontinue from study. The duration of the mitigation plan should not exceed 2 weeks.

- Topical antibiotic or antifungal treatments can be used after consultation and at the discretion of the Investigator. Systemic antifungals or antibiotics must be prescribed by the Investigator if necessary to avoid risk of more serious or broader infections.
- Subjects should limit exposure to UV via sunlight and avoid tanning beds.

Table 7 Prohibited Medication and Treatments Including Time Point of Discontinuation

Prohibited Medication	Time Point of Discontinuation

 • Topical retinoids • Topical prescription or over-the-counter therapies 	2 weeks before Visit 2 (Baseline)

 • Keratolytics • Topical corticosteroids 	5 days before Visit 2 (Baseline)

 • Bland emollients 	
 • Visit 2 (Baseline) – for Optional Maximal Use arm • Visit 4 (Week 4) – for Phase III study
• Over-the-counter low potency hydrocortisone	Visit 2 (Baseline)
Prohibited Systemic Treatment	Time Point of Discontinuation

 • Systemic retinoids 
 ◦ Isotretinoin ◦ Acitretin 	
 • 12 weeks before Visit 2 (Baseline) – for Optional Maximal Use arm • 1 year before Visit 2 (Baseline) – for Phase III study • 3 months before Visit 2 (Baseline)

 • Vitamin A supplements • St. John's Wort • Other therapies intended for CI or may improve CI 	4 weeks before Visit 2 (Baseline)
• Immunosuppressive drugs (e.g., systemic corticosteroids)	2 weeks before Visit 2 (Baseline)
Other	Time Point of Discontinuation
• Ultraviolet treatment	4 weeks before Visit 2 (Baseline)

Subjects may not be enrolled in an investigational drug or device study or have used an investigational drug or investigational device treatment within 30 days prior to Visit 2 (Baseline).

Any medication or vaccine (including OTC or prescription medicines, vitamins, and/or herbal supplements) that the subject is receiving at the time of enrollment or receives during the study must be recorded on the eCRF along with:

- Reason for use;
- Dates of administration including start and end dates; and,
- Dosage information including dose and frequency.

The Medical Monitor should be contacted if there are any questions regarding concomitant or prior therapy.

7 DISCONTINUATION OF STUDY TREATMENT AND SUBJECT DISCONTINUATION/WITHDRAWAL

A list of the data to be collected at the time of treatment discontinuation, follow-up and for any further evaluations that need to be completed is given in the SoA ([Table 1](#) and Table 13).

7.1 Temporary Discontinuation (Drug Interruption/Reduction)

A treatment interruption scheme will be allowed if a subject experiences skin AEs or LSRs during the study. Any subjects with an LSR (especially early during treatment) will be encouraged to continue with their study treatment since transient skin irritation is known to develop with topical retinoids, but LSRs may also develop due to the vehicle formulation or other reasons.

As the study medication will be applied to multiple areas of the body (Treatment Area), it is likely that skin LSRs/AEs may only occur in certain body parts or be more severe in certain body parts. Therefore, actions taken to the study medication do not need to be consistent in the Treatment Area. Proper recording in the eCRF of the body part(s) affected and action taken will be important to document all drug interruptions/reductions. It is desirable to make every effort to maintain subjects in the study to allow adequate assessment of efficacy and safety.

The schedule below (Table 8) outlines the recommended action taken to the study medication based on severity and frequency of the LSR/AE. Deviations to this must be reviewed with the Medical Monitor. The most current NIH Common Terminology Criteria Adverse Events (CTCAE), specifically the subgroups of Skin and Subcutaneous Tissue Disorders and grading system will be used to define severity of LSRs/ adverse events.

Table 8 Recommended Actions taken at AE/LSR Occurrence

	Severity	Action to Study Medication
First and Second Occurrence	Grade 1	If currently dosing twice daily (BID), reduce frequency to once a day (QD) in specific affected area(s) for 3 days. Once resolved, reinitiate BID dosing. If currently dosing QD, discontinue for 3 days in specific affected area(s). Once resolved, reinitiate QD dosing.
	Grade 2	Discontinue use in specific affected area(s) for at least 3 days, no more than 7 days. Once resolved, reinitiate to QD dosing for 7 days. If tolerated, then increase to BID dosing.
	Grade 3	Discontinue use in specific affected area(s) for at least 7 days, no more than 14 days. Once resolved, reinitiate at QD dosing. If no resolution after 14 days, permanently discontinue use in the specific area(s).

	Severity	Action to Study Medication
Third Occurrence	Grade 1	Reduce frequency to QD in specific affected area(s) for 3 days. Once resolved, reinitiate BID dosing.
	Grade 2	Discontinue use in specific affected area(s) for at least 3 days, no more than 7 days. Once resolved, reinitiate to QD dosing for 7 days. If tolerated, then increase to BID dosing.
	Grade 3	Permanently discontinue study medication in any/all affected areas
Fourth Occurrence	Grades 1-3	Investigator and subject discuss regarding permanently discontinuing study medication in any/all affected areas.

In addition to modifying the study medication usage, treatment with non-petrolatum bland emollients (e.g., Cetaphil™) and/or low dose topical corticosteroid, could be introduced at Investigator discretion. These treatments should be stopped once the LSR has resolved, and the study medication reinitiated as per the table.

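### Both Grade 2 cells of Protocol Table 8 end at BID whatever the assigned frequency, so a subject randomized to QD maintenance would be moved to BID in the affected area while still being analysed as QD

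*Protocol*

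**What the plan says.** Table 8 has seven action cells, by occurrence and grade. The two Grade 2 cells use identical wording. After a stop of 3 to 7 days in the affected area, each says: "Once resolved, reinitiate to QD dosing for 7 days. If tolerated, then increase to BID dosing". The third-occurrence Grade 1 cell reads: "Reduce frequency to QD in specific affected area(s) for 3 days. Once resolved, reinitiate BID dosing". By contrast, the first/second-occurrence Grade 1 cell has a separate branch for QD subjects: "If currently dosing QD, discontinue for 3 days in specific affected area(s). Once resolved, reinitiate QD dosing". The first/second-occurrence Grade 3 cell ends "Once resolved, reinitiate at QD dosing".

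The scheme covers reactions during the study and makes no exception for Period 3. Its actions are headed as recommended, but Section 7.1 adds: "Deviations to this must be reviewed with the Medical Monitor". Section 6.4 says "The prescribed dosage, timing, and mode of administration may not be changed, except as defined in" Section 7.1, so Table 8 is the permitted route for changing frequency.

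In Period 3 the frequency is a randomized assignment. Section 6.3 states that "eligible subjects in the TMB-001 0.05% treatment group will be randomized (1:1 ratio) to either TMB-001 0.05% QD or BID maintenance treatment", and Table 6 gives the regimen as "then QD or BID for 12 weeks (depending on randomization").

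On the analysis side, SAP 2.1 and 2.2 analyse ITT and PP subjects by planned treatment. SAP 5.3.1, Table 2, applies treatment policy to dose modifications for the Week 24 endpoints. SAP addendum Section 4.0 presents its added Week 24 IGA results by re-randomized treatment.

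**The concern.** The QD versus BID randomization at Week 12 exists to identify the better maintenance frequency (Protocol 4.2; secondary objectives 5 and 6). A rule that sends QD subjects to BID after a resolved Grade 2 reaction moves them to the comparator regimen in part of the Treatment Area, and does so through a section concerned with interruption and reduction.

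Two things are at stake. The first is a dosing instruction that conflicts with the assignment: on the text, keeping such a subject on QD is the departure that needs Medical Monitor review, while moving to BID is compliant. The second is some dilution of the Week 24 contrast, because the subject remains in the QD column.

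**Working it through.** **1. Every cell, read for a subject assigned QD**

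| Cell | Where a QD subject ends up |
|---|---|
| 1st/2nd, Grade 1 | QD (explicit branch) |
| 1st/2nd, Grade 2 | BID, if 7 days of QD are tolerated |
| 1st/2nd, Grade 3 | QD, or permanent stop in the area |
| 3rd, Grade 1 | No instruction: the cell opens with a reduction to QD, which a QD subject cannot carry out |
| 3rd, Grade 2 | BID, if 7 days of QD are tolerated |
| 3rd, Grade 3 | Permanent stop in affected areas |
| 4th, Grades 1–3 | Discussion about permanent stop |

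Two cells direct an escalation and one is silent.

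**2. Doses to the affected area in Period 3**

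Period 3 lasts 12 × 7 = 84 days, so QD means 84 doses. Doses under Table 8 = days before the reaction + 7 (QD restart) + 2 × remaining days. The reaction day and days off are chosen for illustration, the latter within the 3-to-7-day limits.

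- After day 14, 3 days off: 14 + 7 + 2 × 60 = 141. Returning to QD: 84 − 3 = 81.
- After day 28, 7 days off: 28 + 7 + 2 × 42 = 119. Returning to QD: 84 − 7 = 77.
- After day 56, 7 days off: 56 + 7 + 2 × 14 = 91. Returning to QD: 77.

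These counts apply only to the affected area.

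**3. Period 1**

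Induction is 21 days of QD. A stop of 3 to 7 days plus 7 days of QD takes 10 to 14 days. A Grade 2 reaction before about day 11 (21 − 10) or day 7 (21 − 14) could therefore bring BID forward into induction. After a day 1 reaction with a 3-day stop, BID would start 21 − (1 + 3 + 7) = 10 days early, in that area only. The rule is the same in both arms.

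**4. Dilution at Week 24, illustration only**

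The documents give no Grade 2 rate in maintenance. The largest QD arm is 74/2 = 37 (SAP 1.3.2). Assume:

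- share of the QD arm stepped up, q = 5% to 18%, or 0.05 × 37 = 1.9 to 0.18 × 37 = 6.7 subjects. The 18% is the Phase IIb figure for burning/stinging and erythema by Week 12 on 0.05% BID (n=11, Protocol 2.2). It is not restricted to Grade 2, so it is a high stand-in; the 5% has no source;
- share of the Treatment Area stepped up, f = 25% to 100%, with the effect linear in area;
- true QD–BID difference, D = 10 or 20 points.

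Shrinkage = q × f × D:

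- D = 10: 0.05 × 0.25 × 10 = 0.125 to 0.18 × 1 × 10 = 1.8 points.
- D = 20: 0.05 × 0.25 × 20 = 0.25 to 0.18 × 1 × 20 = 3.6 points.

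The 95% half-width for scale is 1.96 × √[(p1(1−p1) + p2(1−p2))/37]. With assumed rates it is 21.9 points at 0.7 vs 0.5, 20.4 at 0.8 vs 0.6, and 22.3 at 0.6 vs 0.6.

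**5. Would the per-protocol repeat remove the subject?**

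SAP 5.3.2.4 repeats the Week 24 IGA analyses on PP. SAP 2.2 requires at least 50% of planned medication, which is a lower limit that extra dosing does not breach, and no major deviation expected to affect efficacy measurements. Following Table 8 is not on its face a deviation. SAP 4.4, however, classes any deviation that could compromise interpretation as major and gives the Sponsor approval of the exclusion file. The outcome is not determined by the text.

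**The case against.** The best defence is that no investigator would read the table this way. Its actions are recommended, Period 3 is open-label so site and subject know the assigned frequency, and the one cell that mentions QD dosing returns the subject to QD. On that view, the step up to BID means restoring the full regimen, and the Medical Monitor can settle doubtful cases. A drafting omission is indeed the likely explanation. But the Grade 2 wording carries no condition, no other section supplies one, and 30 to 40 centers may read it differently.

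Several stronger readings are tempting and are not supported:

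- **That three cells direct escalation.** The third-occurrence Grade 1 cell starts by reducing to QD, so it assumes BID dosing. For a QD subject it is a gap.
- **That the rule forces more drug onto freshly reacted skin.** The step-up needs resolution, 7 days of QD and tolerance. Subjects in QD maintenance come from an arm whose Period 2 regimen was BID, and Protocol 8.5 counts applications as overdose only beyond twice daily.
- **That the as-randomized analysis is itself wrong.** ITT with treatment policy is the stated estimand and a standard choice.
- **That the per-protocol set certainly keeps these subjects.** Sponsor adjudication under SAP 4.4 leaves this open.
- **That safety summaries are misattributed.** The Safety population is analysed as actually received (SAP 2.3), and how a partial-area step-up would be classed is not stated.

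**Conclusion.** The point holds as a wrong dosing instruction in two Grade 2 cells and a missing branch in one Grade 1 cell. It is minor in consequence and worth correcting chiefly because the instruction conflicts with the randomized assignment.

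A reader might infer that the Week 24 QD versus BID comparison is materially biased. The documents do not support that. The step-up is confined to affected areas, its frequency is unknown, and the comparison is descriptive with 95% intervals and no formal inference (SAP 5.3.2). The illustrative shrinkage of about 0.1 to 3.6 points against a half-width of about 20 to 22 rests wholly on assumed q, f, D and response rates; it gives a sense of scale, not an estimate. Phase IIb reactions occurred mostly at Weeks 2 and 4, and maintenance takes only subjects with at least a 1-point IGA improvement at Week 12, so later Grade 2 events may be rarer still.

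The Week 12 primary analysis is essentially unaffected: it precedes Period 3, and the Period 1 gap concerns at most some early BID days in limited areas under the same rule in both arms. Excess dosing would be partly visible in the Period 3 compliance and dose-intensity summaries (SAP 7.1).

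**What to change.** In both Grade 2 cells, replace the final step with: *return to the frequency assigned at that time (BID only if assigned BID)*. The words *at that time* also cover Period 1. In the third-occurrence Grade 1 cell, add the QD branch already used at first/second occurrence: stop for 3 days in the affected area, then resume QD once resolved.

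The wording change is a few words in three cells. It is still a protocol clarification needing the usual IRB/IEC handling, and regulatory approval where applicable (Protocol Appendix 1), at centers in several countries.

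The documents do not say whether Period 3 dosing is complete. If it is, tabulate by randomized maintenance arm the subjects dosed at a frequency other than the one assigned. This needs no new data: Section 6.4 requires regimen departures in the eCRF, and Section 7.1 asks for the body part and action taken.
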